## 6.6. Timing of Outcome Assessments

The frequency and timing of all the relevant study assessments is considered from the time the participant CH kit arrives to 30 days of observation or a met outcome.

Study Task	Timeline
Kit Setup	Day 1
Participant Intake Survey	Day 1 to Day 3
*Daily Survey	Daily
CRA Adherence Checks	Day 1 to Day 30 ongoing
Vital signs captured by CH wearable	Day 1 to Day 30 ongoing
Outcome Verification	Day 1 to Day 30 ongoing and 30 days after observation period ends

\*Daily symptom questionnaire will close if not completed within a given number of hours. Participant will still be able to fill out the following day's daily symptom questionnaire.

Variables collected from study assessments will be generally as follows:

- Demographic – Categorical
- Medical history and medication – Boolean
- Symptom presence – Boolean (“Much better” to “Much worse”)
- Symptom severity – Ordinal categorical

## 7. Statistical Principles

### 7.1. Consideration for Bayesian Methods

Both Bayesian and frequentist statistics will be used in this analysis. In the Bayesian view, a probability is assigned to a hypothesis, while with the frequentist view, a hypothesis is tested without being assigned a probability. The reporting interpretation and semantics of the different methods will be explicitly stated in comparing confidence versus credible intervals.

### 7.2. Confidence Intervals and P values

The level of statistical significance will be set at  $\alpha=0.05$  threshold.

As this study is primarily Bayesian focused, 95% credible intervals will be used for single parameters, and credible regions will be used for multivariate parameters.

Where confidence intervals are appropriate, 95% confidence will be used.

### 7.3. Adherence and Protocol Deviations

A study participant will be considered fully adherent to study protocol if they:

- Wear the CH device for at least 20 hours a day, at least 6 days a week;
- Answer the questions on the tablet at least 6 days a week;
- Return wearable kit and device.

Adherence metrics will be presented in absolute and percentage terms. Both measures will account for how long a participant is in the study. For example, a participant that is observed the entire 30 days will have a possible total of 720 hours (30 days x 24 hours) and 30 answered tablet symptom surveys. This participant's minimum adherence level would be 600 hours of device wear and at least 26 completed symptom surveys. A participant that meets an outcome much earlier due to hospitalization after 7 days would still be considered adherent if prior to hospitalization they wore the device 140 hours and completed 6 symptom surveys.

A summary table will generally be presented with the following variables per participant:

Participant ID
Time in trial (hours)
Hours of CH device observation
Wearable adherence percentage
Time in trial (days)
Number of surveys completed
Survey adherence percentage
Overall study adherence (Y/N)

Following collection all participants this information will be aggregated to the CONSORT flow chart metrics.

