### 7.3.2. Per Protocol Population

- All subjects who adhere to the major criteria in the protocol as defined by adherence of wearing the CH device for 20 hours a day, 6 days a week, answer tablet surveys at least 6 days a week, and return the CH wearable device kit and tablet.
- The adherent per protocol population will be used for BN training and testing.

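### The 600 h minimum wear total in SAP 7.3 does not follow from its rule of 20 h on 6 days a week, which gives 520 h on the basis used for the surveys

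*Combined protocol and SAP*

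**What the plan says.** SAP 7.3 lists three conditions for full adherence. The wear condition is "Wear the CH device for at least 20 hours a day, at least 6 days a week". The others are tablet surveys on the same minimum number of days and return of the equipment. The protocol (Study Design) gives the same thresholds, and so does SAP 7.3.2: "wearing the CH device for 20 hours a day, 6 days a week".

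SAP 7.3 then works two examples.

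- A participant observed for the full 30 days has "a possible total of 720 hours (30 days x 24 hours) and 30 answered tablet symptom surveys", and the "minimum adherence level would be 600 hours of device wear and at least 26 completed symptom surveys".
- A participant hospitalized after 7 days still counts as adherent if "prior to hospitalization they wore the device 140 hours and completed 6 symptom surveys".

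A per-participant summary table follows. Its wear columns are total hours and a percentage; it has no count of days with 20 h or more. It ends with a yes/no flag for overall adherence, and "this information will be aggregated to the CONSORT flow chart metrics". SAP 7.3.2 adds: "The adherent per protocol population will be used for BN training and testing".

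**The concern.** In one sentence the survey minimum allows one missed day in seven and the wear minimum allows none. The hour total is therefore a different criterion from the written rule: it asks for an average of 20 h over every day, where the rule asks for a number of days that each reach 20 h.

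SAP 7.3 does not say whether the yes/no flag comes from the daily rule or from the totals, and the listed wear columns support only the totals. A flag built that way could disagree with the per-protocol definition in 7.3.2, and it would carry into the participant flow diagram. If per-protocol membership were read from the same flag, the training and testing sets would change too.

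The plan also has no convention for part-weeks. These arise in the last 2 of 30 days and whenever observation ends early, since SAP 6.6 ends observation at 30 days or at an outcome. For recovery, the protocol treats participants as compliant if they report recovery on a listed ground, are resuming normal life and ask to leave. SAP 7.3 and 7.3.2 do not carry this over.

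**Working it through.** **Inputs**, all from SAP 7.3: 20 h per qualifying day; 6 qualifying days in 7; 30 days of observation, 720 h possible; stated minima of 600 h and 26 surveys; 7-day example of 140 h and 6 surveys.

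**Reproducing the plan's figures**

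- Surveys, 30 days: 30 × 6/7 = 25.7, rounded up to 26. Surveys, 7 days: 7 × 6/7 = 6. Both match and use the six-in-seven allowance.
- Wear, 30 days: 30 × 20 = 600 h. Wear, 7 days: 7 × 20 = 140 h. Both match only if every day is counted.

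**Wear minimum under the written rule, 30 days**

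| Part-week convention | Qualifying days | Hours at 20 h |
|---|---|---|
| As for the surveys (25.7 rounded up) | 26 | 520 |
| Pro rata, not rounded | 25.7 | 514 |
| Four full weeks, none of the last 2 days | 24 | 480 |
| Four full weeks, one of the last 2 days | 25 | 500 |
| Rolling 7-day windows (5 days off in 30) | 25 | 500 |

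None gives 600 h. On the survey basis:

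- Difference: 600 − 520 = 80 h, and 600/520 = 1.154, so 15% higher.
- Share of possible wear: 600/720 = 83.3% against 520/720 = 72.2%.

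**Seven days:** 6 × 20 = 120 h; 140 − 120 = 20 h, and 140/120 = 1.167, so 17% higher.

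**Can the rule and the total classify a participant differently?**

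- Meets the rule, misses the total: 26 days at 23 h and 4 days without wear give 26 × 23 = 598 h. With no wear on the 4 days off, reaching 600 h takes 600/26 = 23.1 h on each of the other 26.
- Meets the total, fails the rule: 20 days at 22 h and 10 days at 16 h give 440 + 160 = 600 h with 20 qualifying days. Every convention above needs at least 24.
- Seven days: 5 days at 24 h and 2 days at 10 h give 120 + 20 = 140 h with only 5 qualifying days.

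**The case against.** The best defence is that the governing rule is clear. It appears in the protocol, at the head of SAP 7.3 and again in 7.3.2, while the 600 h figure appears only in an illustration. SAP 7.3.2 cites no hour totals. Return of the equipment is also part of adherence and has no column, so the flag cannot come from the table alone, and the table is described only as what will generally be shown. SAP 8.4 says that non-adherence is analysed separately from the modelling. On this view the point is editorial.

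Much of this limits the consequence. The modelling population is defined by the daily rule, so any effect on it is conditional. It does not remove the contradiction: the example states a minimum level, which reads as a threshold, and nothing says that the totals are not to be used for the wear component.

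Three further objections have some force.

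- The 7-day example is worded as sufficient, and 20 h on all 7 days does satisfy the rule. It is the weaker conflict, although 140 h is not sufficient for every pattern of wear.
- The 23.1 h figure assumes no wear on days off. With 10 h on each of the 4 days off, the other 26 need (600 − 40)/26 = 21.5 h; with 7 h, (600 − 28)/26 = 22.0 h. The gap narrows but remains above 20 h.
- SAP 7.3 says that its measures allow for time in the study. That partly covers early exit, but it gives no part-week rule.

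Finally, 520 h used as a total would share the weakness of 600 h: 22 days at 24 h is 528 h with only 22 qualifying days. Any corrected total should therefore be marked as illustrative.

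**Conclusion.** The concern holds. The stated 30-day minimum of 600 h is inconsistent with the rule it illustrates. On the basis used for the surveys beside it the figure is 520 h, a difference of 80 h (15%). The exact value depends on the part-week convention (480 to 520 h), but no convention considered gives 600 h. The 7-day figure of 140 h, against 120 h, shows the same mismatch in a milder form.

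The firm consequence is ambiguity in the adherence flag and the flow counts derived from it. An effect on model training and testing requires the further assumption that per-protocol membership is taken from that flag. The documents give no wear-time distribution, so neither the number of participants misclassified nor the net direction can be computed. This should be corrected before adherence is derived.

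**What to change.** Reconcile the SAP 7.3 examples with the rule in 7.3, 7.3.2 and the protocol, and state that one rule governs both the adherence flag and per-protocol membership.

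- If the daily and weekly rule governs, derive the wear component from the count of days with at least 20 h, add that count to the summary table, and change the worked figures to 520 h for 30 days and 120 h for 7 days, marked as illustrative.
- If the hour totals were intended, say so and amend 7.3.2 to match.
- In either case, state one part-week convention for wear and surveys. It should cover the last 2 of 30 days and observation ended early by hospitalization, recovery or death, and agree with the protocol's statement on exit after recovery.

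The cost is two worked figures, a sentence naming the rule, a sentence on part-weeks and recovery exits and, if the daily rule governs, one column derived from wear data already collected.

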### 7.3.1. Full Analysis Population

- All subjects who receive CH kit
- The participants will be represented in flow diagram and analyzed for where participants systematically dropped out or did not adhere to study protocol. Participant feedback will also be captured and analyzed on this population.

### 7.3.2. Per Protocol Population

- All subjects who adhere to the major criteria in the protocol as defined by adherence of wearing the CH device for 20 hours a day, 6 days a week, answer tablet surveys at least 6 days a week, and return the CH wearable device kit and tablet.
- The adherent per protocol population will be used for BN training and testing.

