## Methods

### Study Design

This study will be broken down into a pilot phase, followed by two stages of data collection. We will recruit, consent, and enroll approximately 2050 participants with a COVID-19 positive test over the course of the study. In the pilot phase and stages one and two, the following methods will apply.

Participants will be asked to wear the Current Health remote patient monitoring device for up to 30 days. Participants will also be provided with a Current Health tablet with an application installed. The tablet is not password protected, but no responses are stored locally, and they are associated with vital signs via the Current Health dashboard. The participant will be asked to complete a welcome survey on the first day of participation. The tablet will remind the participant each day to answer a brief series of questions about their symptoms and decisions on the tablet. The welcome and daily surveys include the content below:

Welcome Survey: Welcome! Today is your first day in Community by Current Health's COVID-19 Study. We need to collect some information about you. We will only ask these questions **one time**. This survey should take **less than 5 minutes to complete**.

Thank you again for taking part in this study. With your help our researchers will gain a better understanding of COVID-19 and be able to predict recovery and progression.

- 1) What is your date of birth?
- 2) What is your sex? Male/Female/other or prefer not to specify

If Female

- 1) To your own knowledge are you currently pregnant?
- 2) Do you have menstrual periods?
- 3) Are you:
  - Pregnant or breastfeeding
  - Taking hormonal birth control
  - Undergoing menopause or post-menopausal - Highly active (working out, training, fitness, etc.)
- 4) When was your last period?
- 3) What is your occupational category? Healthcare (doctor, nurse, dentist, etc.)  
Service industry (food service, grocery, mechanic, plumber, etc.)  
Retail  
Office – able to work from home  
Office – unable to work from home  
Currently unemployed  
Student – remote  
Student – attending class in person
- 4) What is your household make-up?  
Living alone  
Living with people
- 5) Do other members of your household currently have COVID-19? Y/N
- 6) Are any other members of your household enrolled in Community by Current Health's COVID-10 Study? Y/N
- 7) What is your self-identified race/ethnicity?  
White Hispanic

White Non-Hispanic  
 Black or African American  
 Asian  

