## **Data Management & Security**

After participants are identified as being eligible for this protocol, they will be assigned a randomized and unique identifier under which all subsequent data will be stored. The only mechanism for linking this number to the participant will be through a key that is stored within the Current Health Firewall. Only study team members will have access to the key. Consequently, all participant data collected by the Current Health Device will be stored under this anonymized number, and any information linking to participant data collected by Current Health study team members will also be anonymized under this number. The key will be destroyed at the end of the data analysis portion of this study. For the qualitative substudy, all de-identified interviews will be recorded and stored on a HIPAA compliant platform until transcribed. Once the data are analyzed, audio recordings will be destroyed.

Participant data (including daily survey data) are sent to the Current Health cloud-based system when participants are near the transmitter located within their homes. De-identified welcome survey data are collected and stored in Jotform's HIPAA compliant database. No Protected Health Information (PHI) data is transmitted via the wearable, only anonymized raw waveform data. The device will not attempt to transmit data under unregistered/free access wifi systems and will store data for up to ten hours in the absence of the home-based hotspot. The servers (SOC-2 certified AWS data centers) and solutions housed by Current Health meet stringent guidelines for HIPAA security. The Current Health Information Security Management System is ISO 27001 certified, and also 21 CFR Part 11 and HIPAA Compliant.

Current Health has robust security standards that meet HIPAA compliance standards and no identified, identifying data, or key will be shared or transferred.

Internally, all data collected, stored or analyzed at Current Health will be done behind the Current Health firewall. As noted above, no data used for analyses will be identifiable other than by the unique, random participant number assigned at the time eligibility is determined. All computing systems and servers at Current Health used for these study data are HIPAA compliant. Shared drives are password protected, backed up daily on secure servers, and ensure version control.

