## 8.4. Withdrawal and Follow-up

Participants may withdrawal at any time from the study if they no longer wish to wear the CH device and not respond to tablet based questions. The level of withdrawal, non-adherence, and loss of follow-up will be analyzed separately from modeling (7.3). Where possible CRA will capture reasons for withdrawal such as discomfort of continuous wear of device on upper arm. Withdrawal and loss of follow-up will be presented in the modified CONSORT flow diagram.

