## 9. Analysis

### 9.1. Outcome definitions

Study outcomes will be ascertained by the CRA within the study observational period of 30 days or the following 30 days if the participant has not definitively experienced other outcomes of recovery or death.

Primary and secondary outcomes are presented in (5.1) and will be presented as follows.

Description	Variable	Variable Type
Recovery from COVID-19	recovered	Binary: Yes, No
Hospital stay of 24 hours or longer	hospitalized	Binary: Yes, No
ICU admission	icu_admission	Binary: Yes, No
Death	death	Binary: Yes, No

No calculations are necessary to derive primary or secondary outcomes, they all will be directly stated in binary terms.

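### SAP 7.3.2 makes kit and tablet return a condition for entering Bayesian network training and testing, and the supplied SAP plans no test-set performance in the remaining kit recipients

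*Combined protocol and SAP*

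**What the plan says.** SAP 7.3.2 defines the per-protocol population by device wear of 20 hours a day on 6 days a week, and requires participants to "answer tablet surveys at least 6 days a week, and return the CH wearable device kit and tablet". It then says that "The adherent per protocol population will be used for BN training and testing".

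The full analysis population in SAP 7.3.1 is "All subjects who receive CH kit". Its stated uses are the flow diagram, a description of dropout and non-adherence, and participant feedback. SAP 8.4 keeps withdrawal, non-adherence and loss to follow-up apart from modelling. SAP 9.2 (Stage 2) runs 1,000 test participants through the algorithm, names no analysis population and plans no second result.

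On data flow, the protocol's Study Design section says: "The tablet is not password protected, but no responses are stored locally". Its Data Management & Security section says: "Participant data (including daily survey data) are sent to the Current Health cloud-based system" when participants are near the transmitter at home, and that the device "will store data for up to ten hours in the absence of the home-based hotspot". SAP 9.1 says: "Study outcomes will be ascertained by the CRA within the study observational period of 30 days", or in the following 30 days where no definitive outcome of recovery or death has been reached.

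Three other places bear on who is in the modelling set. SAP 7.3 gives worked examples of adherence: 600 hours and 26 surveys as the minimum over 30 days, and 140 hours and 6 surveys for someone hospitalized after 7 days. The protocol's Stage 1 section has the network first developed on all 1,000 training participants and states no adherence limit. The protocol's Ethical issues section makes payment contingent on wear, surveys and return of the device.

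**The concern.** A test-set result is meant to show how the algorithm would perform in people like those it will be used on. When a prediction is made, nobody knows whether the participant will later post the kit back, and admission or death can affect whether that happens. Conditioning the test set on return therefore selects on something that may be related to the outcome, without any gain in input data. A participant with complete uploaded data and a verified hospitalization could be left out because a box was not returned.

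Under SAP 6.4 the model is finalized and deployed if its AUC is significantly above 0.75 with reasonable sensitivity, specificity and calibration. PPV and calibration depend directly on the event rate in the set tested, so unequal retention of events and non-events would bias them. Losing events also widens the interval around the AUC. Because the plan only describes the excluded participants, a reader of the results could not tell whether either had happened.

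The sample size makes no allowance for exclusions. SAP 6.3 derives 1,000 per cohort from 100 events at 10%. The recruitment stop (2,050, SAP 6.4) and the final-analysis trigger (1,000 validation participants observed, SAP 6.5) count participants, not adherent participants.

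**Working it through.** **What return adds to the data.** Survey responses do not stay on the tablet. Wearable and survey data upload from the home, with at most ten hours held on the device away from the hotspot. Study staff ascertain outcomes. The protocol's Background section mentions stored raw waveforms that allow later quality audit, but Data Management & Security says raw waveform data are transmitted. On this description, return could recover at most a short unsent tail of sensor data.

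**The plan's own figures.** 100 events / 0.10 = 1,000 per cohort, which reproduces. Calculation 2: exp((-0.508 + 0.259 ln 0.1 + 0.504 ln 30 - ln 0.05)/0.544) = 755.9, rounded up to 756, which reproduces.

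**Illustration of differential retention.** The documents give no adherence rate, so the rates here are assumptions. They describe total adherence, not return alone. Take 1,000 test participants with 100 events and 900 non-events, and keep 80% of non-events: 900 × 0.8 = 720.

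For AUC = A with e events and m non-events, the Hanley-McNeil standard error is √{[A(1−A) + (e−1)(Q1−A²) + (m−1)(Q2−A²)]/(e·m)}, where Q1 = A/(2−A) and Q2 = 2A²/(1+A). The AUC needed is the smallest A with A − 1.96·SE(A) > 0.75. A two-sided 95% limit is assumed, because SAP 7.2 sets alpha at 0.05 without stating sidedness.

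| Events retained | Set (events/total) | Apparent event rate | SE at AUC 0.80 | AUC needed |
|---|---|---|---|---|
| No exclusions | 100/1,000 | 10.0% | 0.0272 | 0.803 |
| 50% | 50/770 | 6.5% | 0.0382 | 0.822 |
| 60% | 60/780 | 7.7% | 0.0350 | 0.817 |
| 80% (equal) | 80/800 | 10.0% | 0.0304 | 0.809 |
| 90% | 90/810 | 11.1% | 0.0288 | 0.806 |

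The event rate can move either way. Equal retention moves only the precision.

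**Wear-hour examples against the rule.** Over 30 days, 20 hours on 6 days a week is 30 × 6/7 × 20 = 514 hours, or 26 × 20 = 520 hours if days are rounded up to match the 26 surveys. The SAP's 600 hours is 20 × 30, that is, every day. Over 7 days the rule gives 6 × 20 = 120 hours; the SAP's 140 is 20 × 7. The survey counts (26 and 6) do follow the 6-day rule. A participant with 550 hours over 30 days could satisfy the rule and fail the stated minimum.

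**The case against.** The best counter-argument is that return may exclude very few people. The only SAP text that applies adherence to an admitted participant, the 7-day example in SAP 7.3, does not mention return, and the per-participant adherence table there has no return field. Payment depends on return. Adherence is pro-rated up to hospitalization, and the protocol counts participants who report recovery and leave early as fully compliant. This stands in part: the SAP is ambiguous about return for admitted participants, and losses may be small. But 7.3.2 as written still requires return, and it does not carry over the early-recovery rule.

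Testing a wearable algorithm in people who wore the wearable is also a legitimate target. That defends a wear requirement; it does not defend a return requirement, or the absence of a companion result.

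A reader might infer more than the documents support:

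- **That admissions and deaths will be systematically removed, or that performance will be flattered.** Neither follows. No retention rates are given, and no figure here isolates non-return.
- **That training would fall short of the plan's 756.** All four illustrated sets exceed it. The requirement also changes with the event rate: Calculation 2 needs about 615, 667 and 795 at 6.5%, 7.7% and 11.1%, and 770, 780 and 810 are retained. A fixed cut-off of 756 out of 1,000 is therefore not a sound argument.
- **That no all-recipient analysis exists at all.** SAP section 12 refers to a section 9.5 and to added modelling material that the supplied text does not contain. The protocol's Stage 2 section plans a sensitivity analysis and a search for poorly predicted subpopulations, without defining either.
- **That 140 hours is a minimum.** The SAP offers it as a sufficient example; only 600 hours is called a minimum.

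**Conclusion.** The point holds in this form: return of the kit and tablet should not define the modelling population, and the supplied plan lacks a test-set result in the kit recipients whom that definition excludes. It should be fixed before the deployment decision.

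The potential bias is in PPV and calibration, and it arises only if return or adherence differs by outcome. Its size and direction cannot be obtained from the documents. Under the assumed retention rates the apparent event rate runs from 6.5% to 11.1%, and the AUC hurdle rises by 0.003 to 0.019 above 0.803. With equal 80% retention the cost is precision only, a rise of 0.006. These figures rest on the 10% event rate, a two-sided 95% limit and total adherence, so they do not estimate the effect of the return condition itself.

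Two inconsistencies affect the same population. The protocol's all-1,000 training set does not match SAP 7.3.2, although that wording may partly mean before cross-validation splits. The wear-hour examples do not match the 6-day rule.

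**What to change.** 1. In SAP 7.3.2, remove kit and tablet return from the definition of the modelling population, and make it agree with the hospitalization example in SAP 7.3. Return can stay as a logistics and adherence measure.
2. Before the deployment decision, and beside the adherent-set result, report test-set AUC, PPV, Brier score and calibration in all kit recipients who can be scored from pre-outcome data and have a known outcome. Treat missing inputs as unobserved nodes. Report how many recipients could not be scored and how many have unknown outcomes. Bounds that count unknown outcomes as all events or all non-events are optional; they may be too wide to help.
3. Reconcile the protocol's Stage 1 statement on the training set with SAP 7.3.2. Which population to train on is the sponsor's choice, but it should be stated once.
4. Make the 600-hour minimum and the 140-hour example agree with the 20-hours-on-6-days rule (about 514 to 520 hours and 120 hours), or restate the rule.
5. If SAP text outside the supplied document, such as section 9.5, already covers item 2, cross-refer to it in 7.3.2.

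The cost is mostly wording plus one additional test-set analysis. It needs rules for partial sensor data and some effort to obtain outcomes after withdrawal, which the documents do not specify. The required next-of-kin contact and the further 30 days of outcome verification already support that. The downside is noisier inputs and possibly less favourable performance figures.
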